5.2.2 Subject Disposition

The number of subjects screened and the number (percentage) of subjects who failed screening and the reasons for screen failure will be summarized, based on data reported on the Screening Disposition electronic case report form (eCRF). The distribution of the number of subjects enrolled by each site will be summarized.

The number (percentage) of treated subjects who completed the Core Study and who discontinued early from the Core Study will be summarized according to the primary reason for early discontinuation and other reason(s) for early discontinuation, based on data reported on the core study disposition eCRF.

5.2.3 Protocol Deviations

The number (percentage) of subjects with major protocol violations will be summarized. Major protocol deviation criteria include the following:

- Subject is less than 1 month or over 4 years of age at the time of consent/assent.
- Incorrect diagnosis of epilepsy according to the International League Against Epilepsy's Classification of Epileptic Seizures (1981).
- Subject was on more than 1 inducer AED (i.e., carbamazepine, oxcarbazepine, phenytoin) out of the maximum of 4 AEDs allowed.
- Subject stops or interrupted any approved AEDs the subject was on at baseline OR was on >4 AEDs.
- Non-compliance with study drug defined as overall compliance of <80% or >120%. For subjects where treatment compliance cannot be calculated, major deviations as recorded in the protocol deviation log for compliance will be used.
- Subjects with missing PK data at all PK timepoints, except when a subject was discontinued early from the study before reaching the first PK visit.

5.2.4 Demographic and Other Baseline Characteristics

The demographics and other baseline characteristics of the Safety Analysis Set will be summarized using descriptive statistics (n, mean, SD, median, minimum, and maximum) for continuous variables, and using numbers and percentages for categorical variables. Continuous demographic and baseline variables include age, weight, height, body mass index (BMI) and body surface area; categorical variables include sex, race, and ethnicity.

5.2.5 Medical History

The number (percentage) of subjects in the SAS reporting a history of any medical condition, as recorded on the eCRF, will be summarized.

Clinical Global Impression of Severity at baseline will be summarized.

Epilepsy-specific medical history (etiology, time from diagnosis to Visit 1, seizure type) will be summarized. A subject data listing of medical history will be provided.

5.2.6 Prior and Concomitant Therapy

Prior and concomitant medications will be assigned an 11-digit code using the World Health Organization Drug Dictionary (WHO DD) drug codes. Concomitant medications will be further coded to the appropriate Anatomical-Therapeutic-Chemical (ATC) code indicating therapeutic classification. The number (percentage) of subjects who took prior and concomitant medications will be summarized on the Safety Analysis Set by Anatomical Therapeutic Chemical (ATC) class (i.e., therapeutic class), and WHO DD preferred term. Prior medications are defined as medications that stopped before the first dose of study drug. Concomitant medications are defined as medications that (1) started before the first dose of study drug and were continuing at the time of the first dose of study drug, or (2) started on or after the date of the first dose of study drug up to 14 days after the subject's last dose.

Prior failed AEDs and AEDs taken at baseline, including the number of AEDs, will also be summarized on the Safety Analysis Set.

5.2.7 Treatment Compliance

Compliance with study medication during the Treatment Phase will be summarized using descriptive statistics. Overall percent compliance will be calculated as follows:

Compliance

$$= \left(\frac{(Wt. t of Study Drug Dispensed [g] - Wt. of Study Drug Returned [g])x \frac{0.5 mg}{mL}}{(No. of Days x Prescribed Daily dose [mg])x \frac{1.07 g}{mL}}\right)x 100\%$$

where 0.5 mg/mL is the perampanel concentration in Fycompa oral suspension and 1.07 g/mL is the density of Fycompa oral suspension

Overall study medication compliance will also be summarized using the categories <80%, 80% to 120%, and >120%.

5.3 Data Analysis General Considerations

5.3.1 Pooling of Centers

Subjects from all centers will be pooled for all analyses.

5.3.2 Adjustments for Covariates

Not applicable.

5.3.3 Multiple Comparisons/Multiplicity

Not applicable.

5.3.4 Examination of Subgroups

All analyses will be provided by age cohort (1 to ≤ 6 months, > 6 to ≤ 12 months, >12 to < 24 months, and 24 to <48 months). Summaries of demography, seizure data, and TEAEs may be further presented by inducer/non-inducer subgroup. Growth parameters (height, weight, thyroid and insulin-like growth factor-1 [IGF-1] parameters) may also be summarized by sex.

5.3.5 Handling of Missing Data, Dropouts, and Outliers

Analysis of percent change and responder rate for the seizure frequency per 28 days during the Maintenance Period will use a last observation carried forward (LOCF) type of imputation. If the overall duration of the Maintenance Period is less than 4 weeks, the diary data from the last 4 weeks during the Core Treatment Phase (Titration Period + Maintenance Period) will be used to calculate the seizure frequency per 28 days for Maintenance-LOCF. Subjects who didn't enter the Core Treatment Maintenance Period would be counted as nonresponders in the maintenance period.

The seizure-free status during the Maintenance Period will only be counted for subjects who complete the Maintenance Period (i.e., those who complete the Core Study). A subject who dropped out early would be counted as 'No' for seizure-free status in the Maintenance period.

5.4 Exploratory Efficacy Analyses

This study is designed to assess PK and provide safety, tolerability and efficacy data in children with epilepsy aged 1 month to less than 4 years. Given the small sample size and lack of placebo or comparator, it will not be possible to draw definitive conclusions regarding the efficacy of perampanel oral suspension for the population in this study. As such, no formal statistical tests will be performed. Summary statistics will be displayed for all efficacy parameters in the Full Analysis Set unless stated otherwise.

The primary analysis will use data from the Pretreatment Phase to calculate baseline 28-day seizure frequency. A secondary analysis will use data from the Pretreatment Phase plus data from the 4 weeks prior to Visit 1 to calculate baseline 28-day seizure frequency. Seizure frequency will be based on the number of seizures per 28 days, calculated as the number of seizures over the time interval multiplied by 28 and divided by the number of days in the interval. Seizure frequency will refer to the overall seizure type, unless stated otherwise, obtained by combining across all seizure types.

Post-baseline data reported only during the **on-treatment** duration will be analyzed. The on-treatment duration is defined as follows:

• For diary data: The duration between the day of first study drug dose and the last

day of study drug dose, inclusive.

• For CGIC data: The duration after the day of first study drug dose up to 7 days after the last study drug dose, inclusive.

5.4.1 Primary Exploratory Efficacy Analyses

The efficacy seizure endpoints are the percent change in 28-day seizure frequency during the Treatment Phase compared to baseline, responder rate during the Maintenance Period, and seizure-free status during the Maintenance Period. The baseline 28-day seizure frequency for the primary analyses will use seizure data from the Pretreatment Phase.

The percent change and responder rate analyses will be based on a subset of FAS including subjects with baseline seizure data from the Pretreatment Phase. The seizure-free status will be performed on FAS and modified FAS including subjects who received study drug and had any seizure frequency data during the Treatment Phase.

5.4.2 Secondary Exploratory Efficacy Analyses

Secondary analyses for the percent change and responder rate endpoints in seizure frequency will use seizure data from the Pretreatment Phase plus the data from the 4 weeks prior to Visit 1 to calculate baseline 28-day seizure frequency.

5.4.3 Other Exploratory Efficacy Analyses

The percent change in 28-day seizure frequency during the Titration Period (no imputation) and Maintenance Period (using LOCF-type imputation described in Section 5.3.5) will also be summarized.

Percent change, seizure free and responder rate in 28-day seizure frequency analyses will also be repeated for each seizure type, as appropriate for subjects who have that seizure type during the baseline. Subjects who develop new seizure types during the study will be summarized by seizure type separately.

CGI-C scores at EOT compared to baseline will be summarized using frequency table. The EOT value is the last non-missing value while on treatment.

5.5 Pharmacokinetic, Pharmacodynamic, Pharmacogenomic, and Other Biomarker Analyses

Perampanel plasma concentrations were obtained from blood samples drawn during treatment. Details of the analysis methods for population PK/PD modeling will not be described in this SAP but will be described in a separate analysis plan.

5.5.1 Pharmacokinetic Analyses

Not applicable.

5.5.2 Pharmacodynamic, Pharmacogenomic, and Other Biomarker Analyses

Not applicable.

5.6 Safety Analyses

All safety analyses will be performed on the Safety Analysis Set. Safety data will be summarized using descriptive statistics (e.g., n, mean, standard deviation, median, minimum, maximum for continuous variables; n [%] for categorical variables). Safety variables include treatment-emergent adverse events (TEAEs), clinical laboratory parameters, vital signs, 12-lead ECG parameters, growth parameters (height, weight, thyroid and insulin-like growth factor-1 [IGF-1] parameters). Study Day 1 for all safety analyses is defined as the date of the first dose of study drug.

5.6.1 Extent of Exposure

The duration of Treatment Phase (Titration Period and Maintenance Period) exposure to study drug will be defined as the number of days between the date of the first dose and the date of last dose of study drug, inclusive. The duration of exposure will be summarized as a continuous variable and by duration categories (>1 day, >1 week, >2 weeks, >4 weeks, >8 weeks, >12 weeks, >16 weeks). The dates of first and last dose of study drug will be determined from the Study eCRF.

The mean daily dose, maximum dose received, last dose, and modal dose for each subject over the Treatment Phase and for each period (Titration, Maintenance) will be summarized. The mean daily dose will be calculated by taking the average of all the doses taken during the time period weighted by the number of days on each dose (i.e., sum of [days on each dose*dose]/during the time period).

5.6.2 Adverse Events

The AE verbatim descriptions (investigator terms from the eCRF) will be classified into standardized medical terminology using the Medical Dictionary for Regulatory Activities (MedDRA). Adverse events will be coded to the MedDRA (Version 25.1 or higher) lower-level term (LLT) closest to the verbatim term. The linked MedDRA preferred term (PT) and primary system organ class (SOC) will also be captured in the database.

A treatment-emergent AE (TEAE) is defined as an AE that emerged during treatment, having been absent at pretreatment (Baseline) or

- Re-emerged during treatment, having been present at pre-treatment (Baseline) but stopped before treatment, or
- Worsened in severity during treatment relative to the pre-treatment state, when the AE was continuous

Only those AEs that are treatment emergent will be included in summary tables. All AEs, treatment emergent or otherwise, will be presented in subject data listings.

Treatment-emergent AEs (TEAEs) will be summarized by age group and by EIAED and non-EIAED. The incidence of TEAEs will be reported as the number (percentage) of subjects with TEAEs by SOC and PT. A subject will be counted only once within a SOC and PT, even if the subject experienced more than one TEAE within a specific SOC and PT. The number (percentage) of subjects with TEAEs will also be summarized by maximum severity (mild, moderate, or severe).

The number (percentage) of subjects with TEAEs will also be summarized by relationship to study drug (related, and not related). The number (percentage) of subjects with TEAEs will also be summarized by the onset periods of Titration, Maintenance, and Follow-up.

The number (percentage) of subjects with treatment-related TEAEs will be summarized by SOC and PT. Treatment-related TEAEs include those events considered by the investigator to be related to study treatment. The number (percentage) of subjects with treatment-related TEAEs will also be summarized by maximum severity (mild, moderate, or severe).

5.6.2.1 Deaths, Other Serious Adverse Events, and Other Significant Adverse Events

The number (percentage) of subjects with treatment-emergent serious adverse events (SAEs) will be summarized by MedDRA SOC and PT. A subject data listing of all SAEs will be provided. A subject data listing of all AEs leading to death will be provided.

The number (percentage) of subjects with TEAEs leading to discontinuation from study drug will be summarized by MedDRA SOC and PT. A subject data listing of all AEs leading to discontinuation from study drug will be provided.

5.6.2.2 AEs of Special Interest

TEAEs of special interest listed below will be summarized by SOC and PT. SMQs will be used to identify relevant terms for the following TEAEs.

- TEAEs suggestive of abuse potential
- TEAEs related to alertness and cognition
- TEAEs related to psychiatric disorders
- TEAEs related to hostility/aggression
- TEAEs related to status epilepticus/convulsions
- TEAEs related to lab abnormalities
- Cardiac and ECG TEAEs

TEAEs related to rash will be identified by medical review and summarized. Falls will be listed by actual dose of onset for the Titration and Maintenance Periods.

5.6.3 Laboratory Values

Laboratory results will be summarized using Système International (SI) units, as appropriate. For all quantitative parameters listed in protocol Section 9.7.1.8, the actual value and the change from baseline to each postbaseline visit and to the end of treatment (defined as the last on-treatment value) will be summarized by visit and by age group using descriptive statistics. Qualitative parameters listed in protocol Section 9.7.1.8 will be summarized using frequencies (number and percentage of subjects), and changes from baseline to each postbaseline visit and to end of treatment will be reported using shift tables. Percentages will be based on the number of subjects with both non-missing baseline and relevant postbaseline results.

Laboratory test results will be assigned a low/normal/high (LNH) classification according to whether the value was below (L), within (N), or above (H) the laboratory parameter's reference range. Within-treatment comparisons for each laboratory parameter will be based on 3-by-3 tables (shift tables) that compare the baseline LNH classification to the LNH classification at each postbaseline visit and at the end of treatment. Similar shift tables will also compare the baseline LNH classification for the highest and lowest value during the treatment period.

Appendix 1 (Sponsor's Grading for Laboratory Values) in Section 13.1 presents the criteria that will be used to identify subjects with treatment-emergent markedly abnormal laboratory values (TEMAVs). Except for phosphate, a TEMAV is defined as a postbaseline value with an increase from baseline to a grade of 2 or higher. For phosphate, a TEMAV was defined as a postbaseline value with an increase from baseline to a grade of 3 or higher. When displaying the incidence of TEMAVs, each subject may be counted once in the laboratory parameter high and in the laboratory parameter low categories, as applicable.

5.6.4 Vital Signs

Descriptive statistics for vital signs parameters (ie, systolic and diastolic BP [mmHg], pulse [beats per minute], respiratory rate [per minute], body temperature [in centigrade]) will be presented by visit and by age group.

5.6.5 Electrocardiograms

Descriptive statistics for ECG parameters and changes from baseline will be presented by visit and by age group.

Shift tables will present changes from baseline in ECG interpretation (categorized as normal; abnormal, not clinically significant; and abnormal, clinically significant) to end of treatment.

In addition, the number (percentage) of subjects with at least 1 postbaseline abnormal ECG result in QTcF during the treatment period will be summarized. Clinically borderline and abnormal ECG results in QTcF will be categorized as follows:

Absolute QTc interval prolongation:

- QTc interval 430-450 msec
- QTc interval >450 msec
- QTc interval >500 msec

Change from baseline in QTc interval:

- QTC interval increases from baseline 30-60 msec
- QTC interval increases from baseline >60 msec

5.6.6 Other Safety Analyses

GROWTH

Descriptive summary statistics of changes from baseline in height, weight, and head circumference will be evaluated for each age cohort and overall. This data will be compared with normative scores to assess clinical relevance.

Absolute and percentile changes from baseline in height and weight will be presented by visit and to EOT. The sex and age specific percentiles are calculated from z-scores based on the 2000 Center for Disease Control Growth Charts for the United States.

Some calculation details are provided in Section 13.2. The average of the 2 height measurements from a visit will be used for these summaries. Changes from baseline to EOT in thyroid function and IGF-1 testing will be summarized.

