3.1.2 Secondary Objectives

- To evaluate the short- and long-term safety and tolerability of perampanel oral suspension, given as an adjunctive therapy, in subjects from 1 month to less than 4 years of age with epilepsy
- To evaluate the long-term effect of perampanel oral suspension, given as an adjunctive therapy, on growth from baseline to end of treatment in pediatric subjects from 1 month to less than 4 years of age with epilepsy

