5 STATISTICAL METHODS

All descriptive statistics for continuous variables will be reported using mean, standard deviation (SD), median, minimum and maximum. Categorical variables will be summarized as number (percentage) of subjects. All summaries will be performed by age cohort (1 to ≤ 6 months, > 6 to ≤ 12 months, >12 to < 24 months, and ≥ 24 to <48 months) and overall, unless stated otherwise.

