13.2 Age and Sex Specific Percentile Calculation for Weight and Height

The following information is from US CDC website: http://www.cdc.gov/growthcharts. To obtain the z-score (Z) and corresponding percentile for a given measurement (X), use the following equation:

 $Z=((X/M)^{L}-1)/LS \text{ when } L\neq 0;$ or $Z = \ln(X/M)/S \text{ when } L=0;$

where X is the physical measurement (e.g. weight, length, or calculated BMI value) and L, M and S are the values from the appropriate table corresponding to the age in months of the child (or length/stature). $(X/M)^{L}$ means raising the quantity (X/M) to the L-th power.

For example, to obtain the weight-for-age z-score of a 9-month-old male who weighs 9.7 kg, we would look up the L, M and S values from the WTAGEINF table found at http://www.cdc.gov/growthcharts/percentile_data_files.htm, which are L=-0.1600954, M=9.476500305, and S=0.11218624. Using the equation above, we calculate that the z-score for this child is 0.207. This z-score corresponds to the 58th percentile.

SIGNATURE PAGE

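### Percentile change is the only norm-referenced growth change the SAP defines, and it hides growth loss in children who start at about z = -2 or below; z-score change should be added

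*SAP*

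**What the plan says.** Growth is a secondary objective (SAP 3.1.2): "To evaluate the long-term effect of perampanel oral suspension, given as an adjunctive therapy, on growth from baseline to end of treatment".

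SAP 5.6.6 plans three things. Changes from baseline in height, weight and head circumference are summarised by age cohort and overall. A comparison with norms is promised: "This data will be compared with normative scores to assess clinical relevance". For height and weight it then names the scales: "Absolute and percentile changes from baseline in height and weight will be presented by visit and to EOT".

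The percentiles come from z-scores: "The sex and age specific percentiles are calculated from z-scores based on the 2000 Center for Disease Control Growth Charts for the United States". SAP 13.2 gives the LMS formula for both quantities: "To obtain the z-score (Z) and corresponding percentile for a given measurement (X), use the following equation". Its title covers weight and height only.

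The statistics are set in SAP section 5: "All descriptive statistics for continuous variables will be reported using mean, standard deviation (SD), median, minimum and maximum". Neither document plans a summary of the z-score or of its change. The method for the normative comparison is not stated in SAP 5.6.6, in Protocol 9.7.1.8 or in the growth paragraph of Protocol Appendix 3.

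**The concern.** The study has one arm, so growth can be judged only against reference children. Absolute change cannot do that unaided: children of 1 to 48 months normally gain height and weight, so faltering appears only as a smaller gain, and by how much depends on age and sex. That leaves percentile change to carry the age- and sex-adjusted reading.

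A percentile is bounded at 0 and 100 and flattens towards both ends. The same loss in SD units therefore gives a large point change in the middle of the chart and a very small one near the floor. A child who is already very small can lose substantial ground and barely register in the planned table. The z-score, which treats a given loss alike from any start, is computed on the way to the percentile and then left unsummarised.

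**Working it through.** **Inputs.** The LMS constants and worked example come from SAP 13.2, and the summary statistics from SAP section 5. The documents do not give the baseline z distribution, so starting scores from 0 to -2.5 and losses of 0.5 and 1 SD are assumptions shown as a range.

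**Step 1: the plan's own example.** For a 9-month-old boy of 9.7 kg the SAP gives the constants "which are L=-0.1600954, M=9.476500305, and S=0.11218624" and concludes "we calculate that the z-score for this child is 0.207".

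- Z = ((X/M)^L - 1)/(L × S)
- X/M = 9.7/9.476500305 = 1.02358, and (X/M)^L = 0.996275
- L × S = -0.0179605
- Z = -0.003725/-0.0179605 = 0.2074, and 100 × Φ(0.2074) = 58.2

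This agrees with the stated 0.207 and 58th percentile. The calculation in 13.2 is sound.

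**Step 2: a fixed loss on the percentile scale.** For a loss of d SD from starting score z0, the percentile change is 100 × [Φ(z0 - d) - Φ(z0)].

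| Start z0 | Start percentile | Percentile after 1-SD loss | Change, 1-SD loss | Share of change from median | Change, 0.5-SD loss |
|---|---|---|---|---|---|
| 0 | 50.0 | 15.9 | -34.1 | 100% | -19.1 |
| -1 | 15.9 | 2.3 | -13.6 | 40% | -9.2 |
| -1.28 | 10 | 1.1 | -8.9 | 26% | -6.3 |
| -1.64 | 5 | 0.4 | -4.6 | 13% | -3.4 |
| -2 | 2.28 | 0.13 | -2.1 | 6.3% | -1.7 |
| -2.5 | 0.62 | 0.02 | -0.6 | 1.8% | -0.5 |

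On the z scale every row reads -1.00 or -0.50.

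**Step 3: the compression belongs to the scale, not to the child.** Inverting the SAP's formula for the same 9-month-old boy, X = M(1 + L × S × Z)^(1/L), a 1-SD shortfall is 1.00 kg from the median, 0.77 kg from z = -2 and 0.73 kg from z = -2.5. The shortfall at z = -2.5 is 73% of that at the median in kilograms, but 1.8% of it in percentile points.

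**Step 4: effect on a group summary (illustration).** Take a group with half the children at z = 0 and half at z = -2.5.

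| Who loses 1 SD | Mean z change | Mean percentile change | Minimum z change | Minimum percentile change |
|---|---|---|---|---|
| The half at z = -2.5 | (0 - 1)/2 = -0.50 | (0 - 0.60)/2 = -0.3 | -1.00 | -0.6 |
| The half at z = 0 | (-1 + 0)/2 = -0.50 | (-34.13 + 0)/2 = -17.1 | -1.00 | -34.1 |

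The same average loss reads as almost nothing or as 17 points, depending on which children lose it. The minimum behaves in the same way.

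**The case against.** The best defence is that percentile change does not stand alone. SAP 5.6.6 also plans absolute change and a normative comparison, section 5 lists the median, minimum and maximum besides the mean and SD, and the table shells are in a separate document (SAP section 11). An outright loss of weight would show in the minimum absolute change whatever the starting percentile. Growth failure can also surface as an adverse event, a DMC monitors safety, and no decision rule depends on the percentile table.

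Much of this stands as a limit on the consequence, but it does not remove the defect. Faltering in this age range usually means gaining too little, and absolute change has no reference for that. The normative comparison has no method, so it cannot be assumed to mean z-scores. The median, minimum and maximum of percentile change lie on the same compressed scale, and the minimum tends to pick out a child nearer mid-chart.

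Some stronger readings go too far:

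- **That loss vanishes in any small child.** From z = -1, or from the 10th or 5th percentile, it is reduced but visible.
- **That the cohort tables will conceal a growth effect.** This depends on how many children start near the floor, which the documents do not say. The 4 kg entry minimum excludes the smallest of the youngest infants. It does not exclude a 9-month-old boy at z = -3, who weighs 6.83 kg by the SAP's constants.
- **That the cohorts will contain only 5 or 6 infants.** The figures of 6, 5 and 5 are minimums, within 16 to 24 subjects under 24 months.
- **That the long-term growth analysis has the same fault.** This SAP covers the Core Study. The Extension has its own SAP, and Protocol Appendix 3 names no percentile scale.

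**Conclusion.** The point holds as a weakness in the choice of scale, not as an error of calculation. Of the growth changes SAP 5.6.6 defines, only percentile change is referenced to norms, and it shows a 1-SD loss at 6.3% of its mid-chart size from z = -2 and at 1.8% from z = -2.5. Loss in children starting at about z = -2 or below is thus nearly invisible in the percentile summaries, whichever of the five statistics is read.

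The point sizes follow from the normal distribution and the SAP's own conversion and need no further assumption. The effect on this trial's cohort summaries does need one, because no baseline z distribution is given; the group in Step 4 is an illustration, not a forecast. The analysis is descriptive, so what is at stake is how a secondary safety objective is read. The improvement is still worth making, since the better variable already exists.

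**What to change.** In SAP 5.6.6:

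1. Add change from baseline in z-score for height and weight, by visit and to EOT, by age cohort and overall, as the main norm-referenced growth summary.
2. State that this is the comparison with normative scores.
3. Treat head circumference the same way where the reference tables allow, and extend 13.2 to match. At present it has a planned change from baseline but no percentile or z-score.

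Percentile changes can stay as supportive output. A count of children falling by at least 1 z-score unit is optional. The separate Extension SAP should use the same z-score scale, so that Core and long-term growth can be read together.

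The cost is SAP wording and one table shell. The z-score is already an intermediate variable for height and weight, and head circumference is already measured, so no new data are needed.
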